3.2.1 Primary outcomes

Primary outcomes will be the change in bacterial load compared to baseline. (see appendix A – molecular microbiology protocol for details on quantification). [name] laboratory at UM Miller School of Medicine, Department of Dermatology and Cutaneous Surgery will be the coordinating center responsible for tissue sample receipt and

processing. Bacterial load in CFU/g among treatment and control arms will be calculated for each wound at visits T0, T2 and T3. The trajectories of bacterial load for each subjects and average change in bacterial load between groups will be compared.

3.2.2 Secondary outcomes

Secondary outcomes will include:

Microbiological outcomes: bacterial silver resistance characterization on molecular and phenotypic level over time (see appendix A for molecular microbiology protocol).

Clinical wound outcomes: healing rate and percent reduction in area over 6 weeks will be calculated by measuring wound area at each visit and dividing the area change by 6 to calculate average wound healing rate in cm^2/week and the average percent reduction for each study arm.

Complete healing at 6 weeks – the proportion of subjects in each study arm in which the study ulcer achieved complete healing at visit F1.

Pain related outcomes: pain assessments will be collected at every visit using visual analog scale (VAS) and time from visit T0 to clinically meaningful decrease in pain (i.e. 33% reduction from baseline) [21] will be calculated. Additionally, time to first indication of no pain will be calculated (i.e. VAS < 5mm)

Quality of life measurements: the EQ-5D-5L [22] and the Wound Quality of Life (WQoL) [23, 24] instruments will be used and assessments take place at visits T0, T4 and F1.

Safety outcomes: adverse events will be recorded at every visit and type and frequency logged and compared between arms.

4. Study population

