The promise of DACC technology. Dialkylcarbamoyl chloride (DACC)- coated dressings are a recent addition to wound care armamentarium. This innovative antimicrobial technology can be imbedded into various dressing and wound care products. Key to its mechanism of action, DACC, a fatty acid derivative is highly hydrophobic. On the other hand the microorganisms, commonly responsible for colonizing chronic VLU, generally have hydrophobic extracellular surfaces, and will therefore irreversibly adhere to the DACC based dressings [17]. Subsequent dressing changes result in the physical removal of large numbers of bacteria and a decreased microbial load. Since the mechanism of antibacterial action is physical binding followed by removal, there is no risk of bacteria developing resistance [17]. Developing non-silver based wound therapies is important due to reports of silver based toxicity [18]. Additionally, this may prove important as evidence exists for the onset of silver resistance in various, clinically relevant microbes [19]. This may be due to possible overuse of silver-based wound care products and is mediated by plasmid acquisition and other genetic mechanisms highlighting the need to better characterize these mechanisms in VLU [18]. Furthermore, silver and other bactericidal agents result in bacterial lysis at the wound bed leading to endotoxin release to the wound bed as well as other proinflammatory mediators that may drive the prolonged inflammatory state of VLU which has been suggested as a mechanism for the chronicity of these wounds [20]. DACC based dressing results in physical removal of whole bacteria avoiding lysis and the subsequent deleterious effects on the wound. Previous pilot studies utilizing standard microbiology culture based methods have shown efficacy of DACC based dressing (Cutimed® Sorbact®) in reducing bacterial load of VLU when compared to silver based wound dressing [19]. However,

these data are likely underestimating the scope of the problem as only 1-2% of bacterial species can be cultured using culture based methods.

In this study we use advanced molecular and microbiome methods to confirm DACC efficiency in patients with VLUs to help bridge this gap in knowledge. In addition, this exploratory study will add to existing knowledge about silver resistance in VLU and evaluate the effects of DACC treatment on VLU predisposed to be colonized with silver-resistant bacteria.

CONFIDENTIAL

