4.2 Criteria for inclusion

Criteria for inclusion in the study:

1. Adults, 18 years old and older (i.e. age \geq 18 years).
2. Venous leg ulcer (VLU) is present on the leg. VLU shall be full thickness but without exposure of deeper tissues (muscle bone or tendon).
3. If more than one ulcer is present, the largest ulcer meeting criteria shall be designated the study ulcer.
4. If more than one ulcer on the study ulcer limb, study ulcer shall be at least one centimeter from other ulcers.
5. Confirmed venous insufficiency, as documented up to 30 days prior to enrollment (Baseline Day 0), by either: a) Duplex ultrasonography, or b) Principal Investigator (PI) clinical assessment to include clinical signs and symptoms of venous ulcerations (e.g., hyperpigmentation of surrounding skin, varicosities, and/or lipodermatosclerosis).
6. Ankle-Brachial Pressure Index (ABI) exam with value of ≥ 0.80 in the affected limb
7. VLU has been treated with silver based therapy for at least 2 weeks within the previous 6 months.
8. VLU present for at least one month prior to screening visit 1.
9. VLU at least 1 cm in size but not larger than 100 cm².
10. After debridement, study ulcer demonstrates a clean wound bed.
11. If subject is a female of childbearing potential, subject must use at least one method of contraception acceptable by PI such as birth control pills, IUD, condoms, or sexual abstinence. At visit 1 urine pregnancy test must be negative.
12. Subject is able to comprehend all study related procedures and adhere to study schedule.
13. Subject is able to provide written informed consent.

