Prior to performing statistical analyses on quantitative study data, the data will be checked, screened and verified to ensure the integrity of the database. Data screening will focus on several aspects. We will determine the amount, the pattern, and randomness of missing data. We will define outliers as observations that appear to be very high or very low, and decide how to proceed based on the presumed cause. We will identify inconsistencies within a single variable and between variables. Initially, we will perform an explanatory data analysis; visually via graphics/plots and numerically by descriptive statistics with mean, standard deviation for measurements taken on a continuous scale, and frequencies and percentages, various types of cross-tabulations for measurements taken on a categorical scale. Corresponding confidence intervals (CI) for means and proportions will be calculated. To have a better understanding of the relationships among different study measurements, parametric or non-parametric correlation coefficients, bivariate/multidimensional cross-tabulations will be constructed. All the descriptive statistics will be reported for all subjects and by study arm.

The primary endpoint of the study, the bacterial load in CFU/g, will be calculated for each wound at visits T0, T2 and T3 among Study Device and Comparator arms. The difference in means of the bacterial load from T3 to T0 will be calculated and compared between study arms with Student's t-test. To be able to study the trajectories of the bacterial load over time, overall and by study arms, the time series plots will be depicted and repeated measures regression analysis will be performed where time and study arm as the main effects. Types of variance-covariance matrix will be determined by standard statistical procedures. We plan to expand the regression model and include other subject characteristics for additional covariate adjustment. Adjusted regression coefficients and corresponding 95% confidence interval (95%CI) will be reported for the study arm as the main effect in the regression models.

The secondary endpoints such as microbiological outcomes, clinical wound outcomes, pain related outcomes, quality of life measurements, and safety outcomes will be analyzed with similar statistical methods as the primary endpoint.

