This research protocol will provide information that may further the understanding of Cutimed® Sorbact® treatment in accelerating wound healing via changes in microbial load and prevention of silver resistance. The bacterial load is increased in non-healing

VLU and promoting a non-healing wound phenotype. We will also evaluate expression of specific set of silver resistance genes whose expression may be stimulated by prolonged Ag-based therapy. [14]

Tissue Collection Procedure

Debridement tissue samples will be taken from the edge of the wound and will be taken at the initial visit and 2 additional points during the trial. The tissue will be transported in a sterile container on ice to [name] lab immediately after collection. One half of the tissue will directly stored into -80°C freezer for DNA isolation; the second half will be preserved in 80% glycerol for colony isolation using standard microbiology and analyzes of silver resistance on phenotypic level. The initial tissue removed will be considered the baseline and will be noted as T0.

Time Point Definitions

T0 – Pre-Randomization

T2 – Two weeks post-initial application SOC+ Cutimed® Sorbact® or SOC + Acticoat®

T3 – Three weeks post-initial application SOC+ Cutimed® Sorbact® or SOC + Acticoat®

DNA Isolation and qPCR

High bacterial burden ($>10^5$ organisms per gram of tissue), even without the classic signs of infection, is detrimental to healing [1, 10, 29]. Bacteria are routinely isolated from VLU by culturing methods. However, standard microbiology techniques present barriers to accurate microflora quantification because many of the chronic wound bacteria are recalcitrant to growth in a culture and are therefore difficult to identify in this manner [30]; [31]; [1]. The availability of molecular PCR based methods has provided researchers with the capability to examine the bacterial composition of human tissue samples in unprecedented detail. This approach would be utilized to further our understanding of mechanism of action Cutimed® Sorbact® on bacterial populations in VLU.

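### Silver resistance is to be compared between arms without conditioning on T0 status, so a yes/no change score mixes acquisition with loss and cannot isolate prevention

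*Combined protocol and SAP*

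**What the plan says.** Section 3.2.2 lists "bacterial silver resistance characterization on molecular and phenotypic level over time" as a secondary outcome and refers to Appendix A for method. It defines no variable, summary measure or subset.

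The analysis is set in one sentence of Section 7: microbiological outcomes, with the other secondary endpoints, "will be analyzed with similar statistical methods as the primary endpoint". For the primary, "The difference in means of the bacterial load from T3 to T0 will be calculated and compared between study arms" by t-test, supported by a repeated measures regression with time and arm as main effects. Further subject characteristics may be added as covariates, but T0 resistance is not named.

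Three other places bear on the point.

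- **Purpose.** The Rationale in Appendix A says the work may inform "accelerating wound healing via changes in microbial load and prevention of silver resistance".
- **Population.** Inclusion criterion 7 in Section 4.2 requires that the "VLU has been treated with silver based therapy for at least 2 weeks within the previous 6 months". The Background says the study will "evaluate the effects of DACC treatment on VLU predisposed to be colonized with silver-resistant bacteria".
- **Measurement.** Appendix A screens DNA from every sample at T0, T2 and T3 for silE, silP and silS. It classes isolates as resistant by an MIC cut-off of more than 512 mg/liter. Its reporting section also expresses PCR results as Ct values and gene copies, with mean and standard deviation at each time point.

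**The concern.** On a yes/no status per ulcer, an ulcer positive at T0 cannot acquire resistance and one negative at T0 cannot lose it. Averaging the change over everyone nets these two events within each arm. Because the trial selects silver-exposed ulcers, a mixture of T0-positive and T0-negative ulcers is to be expected.

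The statement about prevention concerns acquisition, and acquisition in this sense can be observed only in T0-negative ulcers. An all-subject change score gives no separate estimate of it. Section 7 says the purpose of this pilot is effect estimates for sizing later studies. A net change carried forward as if it were a preventive effect would mis-size a later trial by an amount that depends on T0 prevalence.

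**Working it through.** **Inputs from the documents.** 15 completers per arm (Section 4.1 and Appendix A; the Executive Summary gives a different total, 45, which is a separate matter). The enrolment figure of 35 follows from 30 × 1.15 = 34.5, rounded up. The plan gives no figure for silver resistance: no T0 prevalence, acquisition rate, loss rate or target effect. Every rate below is therefore an assumption.

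**Formula.** Let p be T0 prevalence, a the acquisition rate among T0-negatives and l the loss rate among T0-positives, with C for the silver comparator and D for the device.

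- Mean change in an arm = (1 - p)a - p·l
- Contrast, C minus D = (1 - p)(aC - aD) + p(lD - lC)

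**1. Equal loss in both arms.** Take l = 0.40, aC = 0.30 and aD = 0.05. The at-risk difference is 0.25.

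- p = 0.4, silver: 0.6 × 0.30 - 0.4 × 0.40 = +0.02
- p = 0.4, device: 0.6 × 0.05 - 0.4 × 0.40 = -0.13
- p = 0.4, contrast: 0.15
- p = 0.6: -0.12 versus -0.22, contrast 0.10

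Loss drops out of the contrast, which is simply (1 - p) × 0.25: 0.225 at p = 0.10 and about 0.06 at p = 0.75. The silver arm's own net change of +2 points nevertheless sits beside a 30% acquisition rate among its at-risk ulcers.

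**2. Unequal loss.** Take aC = 0.40 and aD = 0.10, an at-risk difference of 0.30.

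| T0 prevalence | Loss 40% C, 10% D (opposing) | Loss 10% C, 40% D (same direction) |
|---|---|---|
| 0.25 | 0.75 × 0.30 - 0.25 × 0.30 = 0.15 | 0.30 |
| 0.50 | 0.15 - 0.15 = 0.00 | 0.30 |
| 0.75 | 0.075 - 0.225 = -0.15 | 0.30 |

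In the opposing case the preventive effect is masked and then reversed. In the same-direction case nothing cancels, but prevention cannot be told from clearance.

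**3. Chance imbalance at T0.** Section 5.2 does not stratify by T0 status. With 15 per arm, the numbers of T0-positives differ by at least 4 with probability 0.16, 0.19 and 0.20 at prevalence 30%, 40% and 50%. With no dressing effect (loss 40%, acquisition 10% in both arms), 8/15 versus 4/15 positives gives expected changes of (7 × 0.1 - 8 × 0.4)/15 = -16.7% and (11 × 0.1 - 4 × 0.4)/15 = -3.3%, a 13.3-point gap. The standard error of the contrast at 40% prevalence is √(2 × 0.21/15) ≈ 0.17, where 0.21 = 0.22 - 0.10² is the variance of one ulcer's change score. The gap is about 0.8 standard errors: noise that conditioning on T0 would remove, not bias.

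**4. Precision of the separate analysis.** At 40% prevalence about 15 × 0.6 = 9 ulcers per arm are at risk. For 0 of 9 the exact upper 95% limit is 1 - 0.025^(1/9) = 0.336. For acquisition of 40% versus 10%, Fisher's exact test has power of about 33% even with all 15 per arm at risk, and about 10% with 8.

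**The case against.** **The net-change analysis is inferred.** Section 3.2.2 says only that resistance is followed over time, and Section 7 says similar methods, not identical ones. That stands. A reader might infer that the plan commits to a T3 minus T0 change in a binary status; it does not. The alternative reading is that the endpoint is undefined, and the same wording cures both.

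**Resistance need not be binary.** Appendix A also gives gene copies, three genes and potentially several isolates per ulcer. On these a T0-positive ulcer can still gain copies, a further gene or a further resistant isolate. That stands, and it defeats the broader inference that acquisition is visible only in T0-negative ulcers. The argument here is limited to a yes/no ulcer status, which gene detection and the MIC class both invite.

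**Gains and losses do not generally cancel between arms.** Also right. A reader might conclude that prevention would be hidden, but with equal loss it is only diluted, in the right direction. Cancelling between arms needs loss that favours silver.

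**Prevention is one rationale sentence, and net presence of resistance is a legitimate aim.** The Background does propose to study presence of resistance in response to treatment. An all-subject randomised comparison answers that, and should stay. It can also be more powerful: when the device both prevents and clears, the t-test on change had simulated power of 39 to 48% under the case 2 rates, against 3 to 34% for the acquisition comparison.

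**Transitions can be derived anyway.** Section 7 plans cross-tabulations, but does not name T0 by follow-up resistance, and no planned comparison between arms uses it.

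**Conclusion.** The point holds in limited form. As written, the plan has no analysis of silver resistance that conditions on T0 status, so on a yes/no ulcer status it cannot estimate prevention. Depending on loss rates, a preventive effect is diluted by (1 - T0 prevalence), masked, or merged with clearance. Chance T0 imbalance adds avoidable noise.

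The illustrative size is a 15-point contrast in place of 25, resting wholly on assumed rates (40% prevalence, 40% loss in both arms, acquisition of 30% versus 5%). The documents support neither a claim that the planned comparison is biased nor one that it must miss a preventive effect.

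This is a secondary endpoint in an exploratory pilot with no power basis. The change is still worth making, because effect estimates are the pilot's stated product and the data needed are already planned.

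**What to change.** In Section 3.2.2 and Section 7:

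1. Define ulcer-level genotypic resistance as any of silE, silP or silS detected. Report phenotypic resistance separately, and distinguish ulcers not tested from ulcers tested and negative.
2. Keep the all-subject randomised comparison, but condition between-arm models for resistance on T0: T0 status for the yes/no measure, T0 level for gene copies.
3. Add two summaries by arm, each with an exact 95% CI: acquisition at T2 or T3 among T0-negative ulcers, and loss at the last available sample among T0-positive ulcers. T0 tissue is taken before randomisation, so comparing arms within these groups is valid.
4. Give the number lacking T2 or T3 tissue by arm. Appendix A makes the T3 bacterial quantification conditional on area reduction not having reached 75%, so missing T3 results may be related to healing.
5. Base any statement about prevention on the acquisition result, noting that a false-negative T0 sample can look like acquisition.

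The cost is wording and a few tables, with no new visits or samples, since T0 tissue is already screened. The downside is small denominators and wide intervals, such as the 34% upper limit for 0 of 9. The result should be presented as estimation, not as a powered test.

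### Healing rate in cm²/week scales with starting ulcer area, but T0 area is not a named covariate: an avoidable loss of precision, not a bias

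*Combined protocol and SAP*

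**What the plan says.** Section 3.2.2 (clinical wound outcomes) names two area measures: "healing rate and percent reduction in area over 6 weeks will be calculated by measuring wound area at each visit". The rate is obtained by "dividing the area change by 6 to calculate average wound healing rate in cm^2/week", so it is not scaled to baseline area. Percent reduction is. The summary to be reported is the "average wound healing rate in cm^2/week and the average percent reduction for each study arm".

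Section 4.2, item 9, sets the size range: "VLU at least 1 cm in size but not larger than 100 cm²". Section 5.2 randomises 1:1 in blocks and describes no stratification by ulcer size. Section 4.1 aims for 15 completers per arm.

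Section 7 says the secondary endpoints, clinical wound outcomes among them, "will be analyzed with similar statistical methods as the primary endpoint". For the primary endpoint, the change from T0 to T3 "will be calculated and compared between study arms with Student's t-test". In addition, "repeated measures regression analysis will be performed where time and study arm as the main effects". Section 7 then adds: "We plan to expand the regression model and include other subject characteristics for additional covariate adjustment". Those characteristics are not listed. Baseline ulcer area is neither named among them nor excluded.

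Table 1 schedules wound area at T0, before randomisation.

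**The concern.** An absolute rate mixes how well an ulcer responded with how large it was at the start. Where eligible sizes differ widely, most patients with small ulcers can contribute only small values, and a few large ulcers weigh heavily on the arm mean. The analysis that carries over most directly to a single value per patient is the unadjusted t-test, which leaves the size-related spread in the error term.

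Section 7 gives the pilot's purpose as producing effect estimates for sizing later studies. The precision of those estimates is therefore what the trial delivers, and noise that a variable already in hand could remove would pass into the next sample size.

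**Working it through.** **The plan's own figures.** The plan gives no SD, effect size or power for healing rate. Its only sample-size arithmetic is the enrolment of 35 in Section 4.1: 30 × 1.15 = 34.5, rounded to 35 (30 / 0.85 = 35.3 would give 36). The check uses 15 per arm from Section 4.1; Section 7 and Appendix A also use 30 in total, whereas the executive summary says 45.

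**What follows from the definition alone.** Rate = T0 area × fractional reduction / 6.

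- 50% reduction of a 1 cm² ulcer: 1 × 0.5 / 6 = 0.083 cm²/week
- 50% reduction of a 100 cm² ulcer: 100 × 0.5 / 6 = 8.33 cm²/week
- 20% reduction of a 60 cm² ulcer: 60 × 0.2 / 6 = 2.0 cm²/week
- Complete closure of a 5 cm² ulcer: 5 × 1 / 6 = 0.83 cm²/week

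The same proportional response spans a 100-fold range, and a modest response in a large ulcer outranks closure of a small one. The lower limit is printed in cm; it is read here as about 1 cm².

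**Assumed inputs for the size of the loss.** None of these is in the documents.

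- 15 per arm, 4,000 simulated trials per setting, two-sided 5% level
- T0 area log-normal, median 8 cm², log SD 0.8–1.2, limited to 1–100 cm²
- Fractional reduction with mean 40% and SD 25–35%, capped at 100%, and at first independent of area
- Two analyses: a t-test on rate, and a linear model of rate on arm and T0 area

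**Variance and standard error.** With no arm effect, T0 area explains 41–61% of the variance of the rate. The standard-error ratio should be close to √(1 − R²):

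- √(1 − 0.41) = 0.77
- √(1 − 0.61) = 0.62

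The simulated ratio was 0.62–0.77, and repeated runs stayed within 0.59–0.79. If larger ulcers shrink proportionally less, the ratio was 0.89–0.94; it depends on how steep that relation is assumed to be. Since precision goes with 1/SE², the gain is like multiplying the sample by:

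- 1 / 0.6² = 2.8
- 1 / 0.8² = 1.6
- 1 / 0.9² = 1.2

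**Detection of a true 30-point gain in percent reduction (area-independent case).**

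| Analysis | Detection |
|---|---|
| Rate, t-test | 15–29% |
| Rate, adjusted for T0 area | 33–70% |
| Percent reduction, t-test | about 61–89% |

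**Wider assumptions.** A separate set used log-normal, log-uniform and uniform areas, with SD of reduction 20–50%. T0 area then explained 8–75% of the variance. It was 8–37% when that SD was 40–50%. For a 20-point difference (log-normal and log-uniform areas, SD 20–40%), power for the rate rose from 0.09–0.18 to 0.13–0.54 with adjustment. A t-test on percent reduction gave 0.26–0.76.

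**Chance imbalance and validity.** With arms of 15, the larger mean T0 area was typically 1.24–1.35 times the smaller (median ratio). In the median-8 settings, the two largest ulcers typically held 33–41% of an arm's total baseline area. Type I error of the unadjusted t-test was about 0.03–0.05.

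**The case against.** The strongest reply is that the plan already covers this. Section 7 intends covariate adjustment, extends similar methods to the secondary endpoints, and allows transformations and model diagnostics. A reader might infer from the t-test that no adjustment is planned; the text does not support that. What stands is narrower. The covariates are unnamed, so nothing ensures that T0 area is among them, and a covariate chosen after the data are seen does not secure the gain in advance.

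Second, percent reduction sits in the same sentence of Section 3.2.2. It is scaled to baseline and, under the assumptions above, detects a difference more often than the adjusted rate does. This stands: the trial keeps a usable area comparison whatever happens to the rate. It does not make the unadjusted rate a good analysis, and the rate will still be reported. Ranking percent reduction above the rate, among secondary outcomes that the plan does not rank, would be closer to a preference.

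Third, this is a secondary outcome in a pilot with no power calculation, so detection percentages are a weak yardstick. That is fair. The standard-error ratio is the better measure, because it bears directly on the effect estimates the pilot is meant to supply.

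Finally, a linear T0-area term does not stop the spread of the rate from growing with ulcer size, so large ulcers keep some extra weight. This is also true; adjustment reduces the problem without removing it.

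**Conclusion.** The point holds as a matter of precision and prespecification. Healing rate in cm²/week depends on starting area by construction, the eligible range is wide, allocation is not balanced on size, and T0 area is not a named covariate. Adjusting for it reduces the standard error to about 0.6–0.8 of the unadjusted value if percent reduction is unrelated to size, and to about 0.9 if larger ulcers shrink proportionally less.

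Two stronger readings are tempting and should not be drawn. One is that ulcer size, rather than the dressing, determines most of this outcome. The documents give no area distribution, no SD and no relation between size and healing, and the variance share falls on either side of one half depending on what is assumed. The other is that the comparison is biased. Randomisation protects it on average, and type I error is not inflated in the simulations.

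All sizes rest on the assumed inputs. The direction does not: adjustment lowered the standard error and raised power in the settings examined. It is a modest improvement to a secondary outcome, worth making because it is free.

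**What to change.** In Section 7, state that the arm comparison of healing rate will use a linear model with study arm and T0 (pre-randomisation) ulcer area as a prespecified covariate, in place of the unadjusted t-test. Report the adjusted arm difference with its 95% confidence interval, and read it beside percent reduction. T0 area should come from the same measurement method (ruler or imaging, Section 5.14) as the follow-up area.

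If log area is modelled on log baseline area instead, state a rule for healed ulcers, whose area is zero and has no logarithm. Under the assumed inputs with a 30-point gain, about 11–20% of treated ulcers close: 0.11 × 15 = 1.7 to 0.20 × 15 = 3.0, or roughly 2–3 patients in that arm.

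The cost is one sentence in Section 7 and one degree of freedom. No new measurement, visit or patient is needed.

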5.12 Pain assessment

Pain is a stated outcome in this study. The intensity of pain at the study ulcer is to be assessed at every visit using VAS. The Visual Analog Scale is a validated pain assessment tool.[25] It is critical that pain assessment be conducted prior to removal of any dressing or compression system and prior to any physical manipulation of the limb. Pain assessments are conducted in all phases of the study as detailed in the schedule of assessments.

The VAS scale is 100 mm in length and only original copies placed in the subjects' source docs a priori are to be used. Photocopy of the scale may jeopardize measurements and later data analyses and therefore only the originals should be used. The scale marks the words "no pain" by the left end of the horizontal bar and "The worst pain I can imagine" by the right end of the bar. At each assessment the subject is asked to mark the level of

current pain by marking a notch along the bar. The distance from the left end of the bar to the notch is measured and recorded at each assessment.

For analysis and interpretation the following categories will be used:

- 0 - <5 mm - no pain
- 5 - <45 mm - mild pain
- 45 - <75 mm - moderate pain
- 75-100 mm - severe pain

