6.3 Handling missed visits

It is preferred that subjects are seen at regular intervals. However, this may not be possible at times. If a subject needs to miss a visit, every effort should be made to reschedule as close as possible to the original date and then resume following visits at the original intervals. For example, if a subject regularly visits on Wednesdays and will miss a visit and a makeup visit is scheduled for that Friday, the next visit should return to the original intervals and be scheduled for the next Wednesday.

6.4 Stopping rule:

The PI may decide to stop the trial due to safety concerns at any time during the trial. The PI may consult the local Institutional Review Board (IRB) and/or Sponsor for safety related decisions.

7 Statistical methods

This study is a single center randomized longitudinal pilot study to investigate the effectiveness of Cutimed® Sorbact® (Study Device) compared to Comparator (silver impregnated contact layer dressing - Acticoat®) in modifying bacterial load in venous leg ulcers (VLU). Efficacy will be measured as the difference in change in bacterial load compared to baseline between two study arms i.e. Study Device vs. Comparator. This study will also

compare bacterial silver resistance based on genetic and phenotypic characterization over time, healing rate, complete healing at 6 weeks, pain, quality of life (QOL) measurements and adverse events as secondary endpoints.

We expect to study n=30 subjects for both the primary and secondary endpoints. The number of subjects estimated for the study (n=30) is not based on hypothesis driven statistical power calculation. Rather, as a pilot study, a goal for this investigation is to generate effect estimates that will assist in determining an appropriate sample size for future studies.

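### Neither pain-time outcome sets a minimum T0 pain: subjects below 5 mm already meet the no-pain event, and their 33% reduction is undefined or trivial

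*Combined protocol and SAP*

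**What the plan says.** Section 3.2.2 defines two pain-time outcomes. The first is "time from visit T0 to clinically meaningful decrease in pain (i.e. 33% reduction from baseline". The second is "time to first indication of no pain will be calculated (i.e. VAS < 5mm". Neither carries a minimum starting score.

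Section 5.12 describes the instrument: "The VAS scale is 100 mm in length", with no pain at the left end, so 0 mm is a possible score. The same section places 0 to under 5 mm in the no-pain category. On timing, "pain assessments will be collected at every visit using visual analog scale (VAS", and Table 1 shows a score at S1, S2, T0 before randomization, T1 to T4, and F1.

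The eligibility lists (4.2, items 1–13; 4.3, items 1–19) cover the ulcer's age ("VLU present for at least one month prior to screening visit 1"), its size, earlier silver treatment and so on. No item concerns pain.

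Section 7 defines no pain subset: "We expect to study n=30 subjects for both the primary and secondary endpoints". Secondary endpoints, pain included, "will be analyzed with similar statistical methods as the primary endpoint", which means a t-test and repeated-measures regression. Section 7 gives no rule for a zero baseline, for an event already met at T0, for the first visit that can count, or for subjects who never have the event.

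**The concern.** A time-to-event outcome is informative only for subjects who can still have the event when the clock starts. A subject who is pain-free at T0 cannot become pain-free because of a dressing, and has no meaningful pain to reduce by a third. As written, nothing keeps such subjects out of either outcome.

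Two things are at stake. First, the values recorded for these subjects depend on a coding choice that the plan does not make. Second, whatever the coding, they add observations that cannot differ between dressings, which pulls the arms together. Section 7 says that the pilot's purpose is to produce effect estimates for sizing later studies, so a diluted pain estimate bears on that purpose even though no power is claimed.

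**Working it through.** The plan states no sample size, power or event count for the pain outcomes, so there is no figure to reproduce.

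**Step 1. Apply the two rules to each T0 score.** Scores are read in whole millimetres. With T0 score b and later score v, the first event needs (b − v)/b ≥ 0.33; the second needs v < 5.

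| T0 VAS (mm) | No-pain event | Smallest drop meeting 33% |
|---|---|---|
| 0 | already met | 0/0, undefined |
| 1, 2, 3 | already met | 1 mm |
| 4 | already met | 2 mm |
| 5, 6 | not met | 2 mm |
| 10 | not met | 4 mm |
| 45 | not met | 15 mm |
| 75 | not met | 25 mm |

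At 0 mm the coding decides the result. Read as a ratio, no reduction exists. Read as v ≤ 0.67 × b, the condition 0 ≤ 0 is met at once. For the no-pain event, the recorded time is zero if T0 can count, or T1 if only later visits count and the score stays below 5 mm.

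**Step 2. Dilution.** Let f be the share pain-free at T0, p the event rate among subjects with pain, and q the event rate that the coding gives to pain-free subjects, taken as equal in both arms. The arm's rate is f·q + (1 − f)·p, so the difference between arms is (1 − f)(pA − pB) whatever q is. The no-pain outcome has q = 1. The 33% outcome is shown with q = 0.

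The documents give neither f nor p. Assumptions: f from 0 to 30%, and p of 60% against 30%. Arms of 15 come from section 4.1 (the executive summary gives 45 subjects overall; the dilution factor does not depend on this). Event rates serve here as a simple gauge; the plan itself speaks of times.

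Power is approximated, with p̄ the mean of the two rates and two-sided 5% assumed because sidedness is not stated, by Φ{[|pA − pB| − 1.96·√(2p̄(1 − p̄)/n)] / √([pA(1 − pA) + pB(1 − pB)]/n)}. In this formula pA and pB are the rates being compared.

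| f | No-pain rates | 33% rates | Difference | Power, everyone (no-pain / 33%) | n per arm if restricted | Power, restricted |
|---|---|---|---|---|---|---|
| 0% | 60 v 30 | 60 v 30 | 30 points | 37% / 37% | 15 | 37% |
| 10% | 64 v 37 | 54 v 27 | 27 points | 31% / 32% | 13.5 | 34% |
| 20% | 68 v 44 | 48 v 24 | 24 points | 26% / 27% | 12 | 31% |
| 30% | 72 v 51 | 42 v 21 | 21 points | 21% / 23% | 10.5 | 27% |

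With 50% against 30% instead, the 20-point difference becomes 18, 16 and 14 points at f of 10%, 20% and 30%.

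**Step 3. Chance imbalance.** The number pain-free in each arm is taken as binomial(15, f), independently. For f of 10%, 20% and 30%, the arms differ by two or more such subjects with probability 35%, 49% and 55%, and by three or more with probability 12%, 25% and 32%.

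**The case against.** The documents do not say that pain-free subjects are included. Inclusion is inferred from the absence of any rule and from the general figure of 30 subjects for all endpoints. That is correct, but no other analysis set is offered, so inclusion is the default.

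A reader might go further and infer that a pain-free subject counts as an instant success on one outcome and a permanent failure on the other. The documents do not support this. Permanent failure arises only at exactly 0 mm and only under one coding; at 1–4 mm the 33% rule is easily met. Instant success requires T0 to count as an event visit, which is not stated.

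A reader might also infer that the arm comparison would reflect the number of pain-free subjects in each arm instead of the dressing effect. That is too strong as well. Allocation is randomized, so imbalance favours neither arm in expectation, and step 2 shows that most of an assumed contrast survives. Nor is there a basis for saying that medians or responder proportions would be shifted, since the plan states neither summary for pain.

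Two further points stand in part. The gain in power from restriction is modest, in a pilot whose size is expressly not power-based. Section 7's repeated-measures regression with covariates, extended to the secondary endpoints, already comes close to an analysis of VAS in everyone, but it does not name T0 VAS as a covariate. It also leaves the two time outcomes undefined for the subjects at issue.

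**Conclusion.** The point holds as a minor one. Neither pain-time outcome has a minimum T0 score, and no criterion requires pain. Subjects below 5 mm at T0 therefore meet the no-pain event before treatment, while their 33% reduction is undefined at 0 mm or met by 1–2 mm at 1–4 mm. The consequence is dilution and chance noise, not systematic bias towards either dressing.

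The size depends on a share that the documents do not give. At an assumed 10–30% pain-free, the contrast keeps 90–70% of its value, so an assumed 30 points becomes 27–21. If nobody is pain-free at T0, nothing is lost. This concerns secondary outcomes of an exploratory pilot; the bacterial-load analysis is untouched.

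**What to change.** Add to section 7:

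- Both pain-time outcomes are analysed in subjects with T0 VAS of 5 mm or more, the protocol's own upper bound for no pain. The number left out is reported by arm.
- T0 is the baseline for pain. This needs saying because section 3.1 also places baseline measurements in the screening phase, where VAS is recorded at S1 and S2.
- Events count only from T1 onward.
- Subjects without the event are censored at their last VAS, and a method that handles censored times is named, since a t-test on times does not.
- VAS over the post-baseline visits is analysed in all subjects by repeated-measures regression with T0 VAS as covariate.

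The last item is needed because the 5 mm floor does not settle everything: a subject at 5 or 6 mm still qualifies on the 33% outcome with a 2 mm drop. Because the T0 score is taken before randomization, restricting on it keeps the comparison randomized.

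The cost is a change of wording. No visit or measurement is added. The downside is fewer subjects in the two time outcomes, about 1.5 to 4.5 per arm under the assumed 10–30% (0.10 × 15 and 0.30 × 15).
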